Due to the potential pain and skin injury that can be incurred with travel for participants with more severe EB subtypes, this trial is intentionally designed to minimize the number of in-person clinic visits through use of home itch diaries and phone follow-up, as recommended by the FDA in their EB-specific guidance document.⁴

7. Efficacy Endpoints:

Based on the data from our pilot study, the primary statistical endpoint will be the proportion of participants who achieve at least a 3-point reduction in average daily NRS itch severity from baseline at the end of the two-month double-blind phase.

Secondary endpoints will include:

1. Comparative weekly change in daily worst-itch NRS during the double-blind phase
2. Safety, as measured by adverse events during the course of the double-blind and open label phases of the trial. These will also include changes in ECG parameters and safety labs following drug exposure.
3. Comparative weekly change in average daily NRS itch severity during the double-blind phase
4. Proportion of participants who achieve at least 2 and 4-point reductions in average daily NRS itch severity from baseline at the end of the double-blind phase
5. Proportion of participants who achieve at least a 30% or 50% reduction in average daily NRS itch severity from baseline at the end of the double-blind phase
6. Change in participant-reported outcomes of global assessment of change in itch and overall improvement as measured by static participant assessment of itch, participant global assessment of change in itch severity, and caregiver global assessment of change in itch severity.

The Stanford EB Itch Survey also captures additional measures related to symptoms during dressing changes, sleep quality, and other quality of life measures which may be explored.

Additional exploratory endpoints will revolve around mean comparative change in wound surface areas, comparative change in NRS itch severity at target wounds, and the change in median NRS score by group from baseline at month 1, month 2, and month 3.

We will also assess participant and caregiver perceived change in wound size and number, and pain as measured with the Wong-Baker FACES⁵ scale, and changes in quality of life assessed with ItchyQoL,⁶ and the Dermatology Quality of Life Index (DLQI).⁷

Further exploratory analysis comparing multiple pruritus-related instruments will be explored to determine the most appropriate measures of pruritus for this participant population.

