The proportion of participants achieving 2, 3, and 4-point reductions in average daily NRS with serlopitant at the end of 8 weeks of active treatment will be compared to placebo using Fisher's Exact test. A similar approach will be utilized to compare the proportion of participants achieving at least a 30% or 50% reduction in itch as measured by NRS from baseline at 8 weeks.

We will also measure continuous change in average daily NRS and worst-itch NRS score by group over time. For each participant, we will plot their average itch scores over time before and after drug intervention. For each dosage group, we will use linear regression methods with mixed effects (GLM, SAS) to track the change in itch in each of the groups from baseline.

Furthermore, we will evaluate monthly change in median NRS itch scores by group as compared to baseline, which will enable evaluation of durability through assessment of NRS itch scores at month 3 of washout.

Primary and secondary endpoints will be performed on an intention to treat basis. This study will provide the effect size, standard deviation and range of itch scores in EB participants in order to properly power a phase 3 trial.

11. Safety Assessment and Monitoring

11.A. Pregnancies and Contraception Requirements for Females

For the purposes of this study, a female of childbearing potential is defined as any female who has experienced menarche and is pre-menopausal, unless permanently surgically sterile (e.g., hysterectomy, bilateral salpingectomy, bilateral oophorectomy). A postmenopausal state is defined as no menses for 12 months without an alternative medical cause in a previously menstruating female. We note that many adolescents with severe subtypes of epidermolysis bullosa have may significantly delayed age of menarche.

For the purposes of this study, all female participants of childbearing potential must use highly effective contraception (i.e. pregnancy prevention method with a failure rate of <1% per year) from the time of the Screening visit until 2 weeks after the last dose of study drug. This includes the use of one or more of the following acceptable methods:

1. Surgical sterilization (e.g., bilateral tubal occlusion or ligation, hysterectomy, bilateral salpingectomy, bilateral oophorectomy).

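### Secondary endpoints 1 and 3 are between-arm weekly changes, but the only model stated for them is fitted per dosage group against its own baseline and names no arm-by-time contrast

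*Combined protocol and SAP*

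**What the plan says.** Section 7 lists as secondary endpoint 1 "Comparative weekly change in daily worst-itch NRS during the double-blind phase" and as secondary endpoint 3 "Comparative weekly change in average daily NRS itch severity during the double-blind phase". Both are between-arm quantities.

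Section 10.C, the statistical plan for efficacy endpoints, treats its outcomes in two ways:

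- **Responder proportions.** The 2-, 3- and 4-point responder proportions "at the end of 8 weeks of active treatment will be compared to placebo", with Fisher's exact test named.
- **Scores over time.** Here the plan says "We will also measure continuous change in average daily NRS and worst-itch NRS score by group over time". The model sentence is "For each dosage group, we will use linear regression methods with mixed effects (GLM, SAS) to track the change in itch", and the same sentence gives its purpose as "to track the change in itch in each of the groups from baseline". For each participant, "we will plot their average itch scores over time before and after drug intervention".

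Section 10.C also describes a monthly change in median NRS. That too is by group against baseline, and Section 7 lists it as exploratory. The section then states that primary and secondary analyses are by intention to treat, and adds "This study will provide the effect size, standard deviation and range of itch scores in EB participants" for the purpose of powering a phase 3 trial.

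**The concern.** The endpoint and the model do not match. The endpoint is a difference between arms in weekly change, while the model describes each arm's change from its own baseline. A within-arm change mixes any drug effect with placebo response and with regression to the mean, which is plausible here because entry requires an average NRS of at least 5.

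Two further choices are left open, and both affect the result:

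- **Random effects.** Writing GLM beside mixed effects does not say whether participants have their own slopes or only their own intercepts. With up to 56 daily scores per person, that choice determines whether the standard error of a slope contrast is right.
- **Role of pre-drug scores.** Section 9.B.ii requires at least 7 pre-drug diary days when screening and baseline are combined. The plan does not say whether those scores enter the model as outcomes, as a covariate, or both.

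At stake are the estimate, interval and test for two secondary endpoints, and any slope effect size and SD carried into phase 3 planning.

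**Working it through.** **The plan's own figure.** The plan gives no effect size, SD or power for the longitudinal endpoints. The one related figure is the pilot result in Section 5, a comparative reduction of 0.08 point/week (p=0.11). Over 8 weeks, 0.08 x 8 = 0.64 points, as Section 5 states.

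**Does the stated model estimate the endpoint?** Let b_A and b_P be the weekly slopes in the active and placebo arms. The endpoint is b_A - b_P. The model sentence delivers b_A and b_P separately. No arm-by-time term, difference, test or interval is named for them, whereas the responder analysis in the same section names both a comparator and a test.

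**Is precision lost by fitting per group?** Let s be the total SD of participants' estimated slopes, with 20 per arm.

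- Per-arm SE = s/sqrt(20). SE of the subtracted slopes = sqrt(s^2/20 + s^2/20) = s x sqrt(2/20), which is also the SE of the joint contrast.
- The documents give no s. If the pilot p=0.11 is two-sided and came from a valid participant-slope SE with 7 per arm, s = 0.08/1.726/sqrt(2/7) = 0.087 (t, 12 df) or 0.08/1.598/sqrt(2/7) = 0.094 (normal).
- The per-arm SE is then 0.0195-0.0210 and the SE of the difference 0.0275-0.0297 by either route. Nothing is lost; what is missing is the named contrast.

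**What if participant slopes were omitted?** Assumptions: 56 complete daily scores, independent residuals with SD r of 1.0 or 1.5, true slope SD u of 0.05, 0.10 or 0.15 per week, and no arm difference.

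- Sum of squares of time, in weeks: S = 56 x (56^2 - 1)/12/49 = 298.6.
- True variance of one participant's fitted slope: V = u^2 + r^2/S.
- Variance that an intercept-only model attributes to it: M = (r^2 + u^2 x S/55)/S.
- Type I error is approximately 2 x [1 - Phi(1.96/sqrt(V/M))].

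| u | r | V | M | sqrt(V/M) | Type I error |
|---|---|---|---|---|---|
| 0.05 | 1.5 | 0.01004 | 0.00758 | 1.15 | 0.09 |
| 0.05 | 1.0 | 0.00585 | 0.00340 | 1.31 | 0.14 |
| 0.10 | 1.5 | 0.01754 | 0.00772 | 1.51 | 0.19 |
| 0.10 | 1.0 | 0.01335 | 0.00353 | 1.94 | 0.31 |
| 0.15 | 1.5 | 0.03004 | 0.00795 | 1.94 | 0.31 |
| 0.15 | 1.0 | 0.02585 | 0.00376 | 2.62 | 0.45 |

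A simulation of 4,000 trials per setting agrees: 0.085-0.136, 0.193-0.316 and 0.310-0.451 at the three slope SDs, against 0.046-0.053 when participant slopes are fitted.

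**Does the role of pre-drug scores matter?** Suppose, as an assumption, that a 0.64-point effect arrives all at once at first dose and is then constant. With k pre-drug days and 56 post-dose days fitted as outcomes, N = 56 + k. The least-squares slope per week is 7 x 0.64 x 56 x (k/2) / [N(N^2 - 1)/12].

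- k = 0: slope 0.
- k = 7: 7 x 0.64 x 196/20,832 = 0.042 per week.
- k = 30 (Section 9.B allows up to 30 days from screening to baseline): 7 x 0.64 x 840/52,997.5 = 0.071 per week.

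A steady post-dose effect of 0.08/week reads as 0.080, 0.077 and 0.057 in the same three cases. The estimate therefore depends on a choice that the plan does not state.

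**The case against.** The strongest reply is that the intent is not in doubt. Section 4 says itch relief is evaluated against placebo, Section 7 calls both endpoints comparative, and Section 5 reports the pilot as a between-arm slope difference. An analyst would subtract the slopes and lose nothing. All of this stands, and it is why the point is minor. Intent still does not supply the contrast, its interval and test, the random effects or the role of baseline, and the pilot model is not described.

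A reader might infer more: that the sponsor will present a within-arm fall as a drug effect, and that false-positive rates of a within-arm test therefore measure the harm. The documents do not support this. No section says a fall from baseline in the active arm will be read as efficacy.

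A reader might also infer that participant slopes will be omitted. The text says mixed effects, and nothing shows that slopes would be left out, so the 9-45% range is conditional on an omission that is possible but not stated.

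Treating baseline as a covariate only is one valid option among several. With post-dose scores alone, a slope misses an immediate effect altogether, so the plan is not wrong to contemplate pre-drug data.

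Finally, the diary items in Section 9.A.v do not include worst itch. Where the endpoint 1 data come from is a separate data-collection question and adds no weight here.

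**Conclusion.** The point holds, at minor size. The model in Section 10.C, followed literally, gives within-arm changes and does not estimate secondary endpoints 1 and 3 as Section 7 defines them. The target is clear and the contrast is recoverable at the same SE, so this is an incompletely specified analysis of a named endpoint. The reach is two secondary endpoints and any phase 3 planning based on the slope. The primary endpoint, the other responder comparisons and the total of 40 are untouched.

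The mismatch itself rests on the text alone. The numerical illustrations rest on assumed slope and residual SDs, complete diaries, independent daily residuals and, for the pre-drug window, an assumed effect shape. They apply to endpoint 3, since daily worst-itch data cannot be assumed.

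**What to change.** Replace the per-group sentence in Section 10.C with one linear mixed model of all randomised participants in both arms, and replace the GLM label with the procedure actually used (SAS PROC MIXED or equivalent). Specify:

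- **Fixed effects:** arm, week, arm-by-week and the EB-subtype randomisation stratum of Section 10.A.
- **Random effects:** an intercept and a slope per participant, with a stated residual covariance for the daily scores.
- **Estimate:** the arm-by-week coefficient, with its 95% CI and a two-sided test at 0.05, as the comparative weekly change. Report the model's arm difference at week 8 with its 95% CI beside it, so that an early effect is visible.
- **Pre-drug scores:** state once whether they enter as a covariate or as outcomes. Either is valid.
- **Time origin:** define it for participants randomised but never dosed, so that the model fits the intention-to-treat statement.
- **Within-arm slopes and plots:** label them descriptive.

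The cost is SAP wording, with no new data for endpoint 3. Use the same model for worst itch once its data source is stated. The change should be made before investigators gain the aggregate data access described in Section 10.A.

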A Neurokinin-1 Receptor Antagonist for the Treatment of Pruritus in
Patients With Epidermolysis Bullosa

Study Protocol and Statistical Analysis Plan

NCT03836001

March 25, 2021

1. Title: A Phase 2 trial of Neurokinin-1 Receptor Antagonist for the Treatment of Itch in Epidermolysis Bullosa Patients

2. PI: [name]

Co-PI: [name], PhD

3. Funding sources for this project:

Epidermolysis Bullosa Research Partnership (EBRP) – providing funding (SPO # [REDACTED])
Menlo Therapeutics, Inc. – providing study medication

4. Abstract:

This is a follow-up study to a prior pilot phase 2 trial conducted here at Stanford and will assess the effect of serlopitant (5 mg daily) on EB-related itch in adolescents (≥ 13 y.o.) and adults with EB. We will evaluate the degree of itch relief in participants taking serlopitant as compared to placebo. This will be determined by comparing the proportion of participants with 3 point or greater reduction in average daily itch severity as measured by numeric rating scale (NRS) score following two months of treatment. Secondary aims include continuous change in average daily NRS and worst itch NRS over time, proportion of participants achieving 2-point and 4-point reductions in average itch severity following two months of treatment and change in median NRS as compared to baseline. Finally, we will assess the safety profile of serlopitant in study participants. It is our hope that serlopitant will reduce itch in adolescents and adults with EB.

5. General background:

Management of chronic pruritus is notoriously challenging for patients with epidermolysis bullosa (EB). In a comprehensive survey of 146 EB patients, itch was reported as the most bothersome EB symptom, ranking higher than acute or chronic pain or problems eating.¹ Furthermore, pruritus can induce an itch-scratch-blister cycle, which can exacerbate existing wounds or induce new wounds.² There have been no new drugs for chronic pruritus, and the current management of pruritus in EB with antihistamines and topical steroids only minimally relieve itch.³

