with any EB subtype. Although the 14 participant trial was only powered to detect large differences in numeric rating scale (NRS) itch scores, we observed a small magnitude reduction in NRS itch score over time in favor of serlopitant relative to placebo (0.08 point/week comparative reduction) although this difference did not meet statistical significance ($p=0.11$). This was equivalent to a 0.64-point reduction in the NRS itch score (rated 0-10) by the end of the active treatment period. In post-hoc analysis, we found a significant majority of participants in the serlopitant arm (86%) experienced at least a 1-point reduction in NRS score by end of treatment. More participants in the active group (43% vs. 14%) achieved at least a 3-point reduction in NRS itch score by the end of treatment as compared to placebo, although this was not statistically significant ($p=0.35$). Serlopitant was well tolerated, with no new safety signals observed.

6. Study design:

This is an investigator-initiated, single-center, randomized, double-blind, placebo controlled, parallel arm trial evaluating the effects of serlopitant at 5 mg by mouth daily on EB-related itch. Eligible participants must have a clinical diagnosis of EB and average daily pruritus rated at least 5 based on a 0-10 Numeric Rating Scale (NRS) persistent for at least 6 weeks.

We aim to recruit at least 40 participants, age 13 and older, of all EB subtypes. Participants will be assigned to placebo or serlopitant in a 1:1 ratio. Participants randomized to serlopitant will receive a loading dose of serlopitant 15 mg PO once, followed by serlopitant 5 mg PO daily for 2 months. This dosing regimen is identical to that investigated during our pilot phase 2 trial.

After completing the double-blind phase of the trial, all participants will undergo one month of wash-out before being offered the option of participating in an open label extension phase with serlopitant 5 mg PO daily for continued monitoring of toxicity and efficacy. This extension phase will be 12 months for participants enrolled prior to May 2020, and 3 months for participants enrolled after May 2020, due to drug availability.

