Labs will ideally be drawn in the morning. At the discretion of the investigator, labs drawn by non-study providers within this time window (2 months after medication initiation, +/- 10 days) may be substituted for the study lab draw, as long as they include the same studies of interest. This is in order to reduce unnecessary skin trauma and a potentially psychologically traumatic blood draw.

Any abnormal labs will be reviewed by investigator and appropriate follow-up will be initiated as needed.

Any clinically significant abnormalities identified in prolactin or thyroid function will be followed until the level returns to baseline or appropriate follow-up can be established with a local provider.

9.D.v. Reminders and Home Diaries:

Participants will be given new daily itch diaries to complete during the wash-out period. They will be reminded to continue to complete their daily diary entries.

Female participants of childbearing potential (including participants that have not yet undergone menarche) who are not using hormonal contraception will be provided with a menstrual diary to complete.

Female participants of childbearing potential will be reminded to continue their acceptable form of contraception until 2 weeks after study drug discontinuation.

9.E. Month 3 Phone Call / End of Wash Out Phase:

One month (30 days, +/- 14 days) after completing the double-blind phase participants will be contacted by phone.

9.E.i. Assessments by Phone:

Participants will be queried for any adverse events and changes to concomitant medications or wound dressing regimen. These will be assessed by investigators. Participants will specifically be asked about any symptoms of adrenal insufficiency (e.g. fatigue, abdominal pain, dizziness, etc.).

Female participants will specifically be queried regarding abnormal vaginal bleeding (new and different from any related to any known EB wounds in the genital area), new breast findings (not related to EB wounds), expulsion of an intrauterine device or implant, or vaginal discharge. If any of these concerns are identified, the participant will be referred to their primary care provider for further evaluation.

9.E.ii. Global Pruritus Assessments by REDCap:

A link will be sent to the participant to complete the following assessments via REDCap:

1. Stanford EB Itch Survey
2. Itch Man

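### Durability is read from the shift in each group's median NRS against baseline, with no requirement that the same participants enter both medians and no within-participant change from Month 2 to Month 3

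*Combined protocol and SAP*

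**What the plan says.** Section 10.C (Statistical plan for efficacy endpoints) states: "we will evaluate monthly change in median NRS itch scores by group as compared to baseline, which will enable evaluation of durability", and continues "through assessment of NRS itch scores at month 3 of washout". No other analysis in the plan is tied to durability.

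The same measure appears in two other places, with different standing:

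- Section 7 (Efficacy Endpoints) places it among the additional exploratory endpoints: "the change in median NRS score by group from baseline at month 1, month 2, and month 3".
- Section 4 (Abstract) includes "change in median NRS as compared to baseline" among the secondary aims. It does not mention durability, Month 3 or wash-out.

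On timing, Section 6 says "all participants will undergo one month of wash-out" after the double-blind phase. Section 9.E places the Month 3 contact at the end of that period: "One month (30 days, +/- 14 days) after completing the double-blind phase participants will be contacted by phone". Section 9.D.v provides for daily data in between: "Participants will be given new daily itch diaries to complete during the wash-out period".

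Section 10.C also plans a plot of scores over time for each participant and a mixed-effects regression of change from baseline. Neither is linked to durability, and the weekly-change endpoints in Section 7 are confined to the double-blind phase. The intention-to-treat statement in Section 10.C covers primary and secondary endpoints. The plan gives no rule for missing Month 3 scores and no expected drop-out rate.

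**The concern.** A change in a group's median and the median of participants' changes are different statistics. The first compares two cross-sections. If some participants give no Month 3 score and the baseline median still includes them, part of the shift reflects who stayed and not how anyone's itch changed. Section 9.G describes an early termination visit for those who leave during the double-blind phase, but no Month 3 score for them. It is also unclear whether the intention-to-treat statement reaches this measure, since Section 7 calls it exploratory and the abstract calls it a secondary aim.

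The reference point matters as well. A change from baseline to Month 3 combines what happened on treatment with what happened after it stopped. A reader who wants to know how much of the Month 2 benefit was kept needs each participant's own change from Month 2 to Month 3, and the plan does not specify it.

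At stake is a descriptive statement about lasting benefit that could be larger or smaller than participants' own scores support, and less precise than the same diary data allow.

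**Working it through.** The plan gives no figure for this analysis, so there is none to reproduce. Only the group size (20 per arm, Section 10.B) comes from the documents. The other inputs below are assumptions.

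**1. The two statistics.** For one arm:

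- As written: D = median(baseline scores) − median(Month *t* scores).
- Paired: P = median over participants of (own baseline − own Month *t* score).

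They need not agree, even when the same people enter both medians.

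**2. Departure alone moves a group median.** Take 20 Month 2 scores: 1, 1, 2, 2, 3, 3, 3, 4, 4, 4, 5, 5, 6, 6, 6, 7, 7, 8, 8, 9. Let every Month 3 score equal the Month 2 score, so that every own change is 0.

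- All 20: median = (4 + 5)/2 = 4.5.
- The 4 highest leave: the middle two of the remaining 16 are 4 and 4, median 4.0, an apparent gain of 0.5.
- The 4 lowest leave: the middle two are 5 and 6, median 5.5, an apparent loss of 1.0.
- The median own change among those seen at both times is 0 in every case.

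**3. The same idea by simulation.** One arm of 20, no individual change, Month 2 mean 5, scores rounded to 0–10.

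| Loss | Result with SD 2.5 and 4 of 20 lost | Range over SD 2 to 3 and 2 to 6 lost |
|---|---|---|
| Random | median moves by 0.5 or more in 42% of trials; mean shift 0 | 24% to 56%; mean shift 0 |
| Loss weight multiplied by exp(0.5) per NRS point | mean shift −0.48 | −0.16 to −0.97 |

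Random loss therefore adds noise only. Itch-related loss adds a systematic shift.

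**4. Change from baseline.** 20 per group, baseline about 6.8 (SD 1.3, limited to 5 to 10), true fall 1.5, SD of change 1.2 to 2.5, change independent of baseline.

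| Scenario | Shift in group medians (D) | Paired median (P) |
|---|---|---|
| 4 highest-baseline participants leave; baseline median uses all 20 | about 1.8 | 1.50 |
| Same loss; both medians use the 16 who stay | about 1.52 to 1.54 | 1.50 |
| 4 lost at random | about 1.47 | 1.50 |
| 4 with the worst follow-up itch leave | about 1.9 to 2.15 | about 1.76 to 2.12 |

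In the first row the excess is 1.8 − 1.5 = 0.3 point, or 0.3/1.5 = 20%. The second row shows that nearly all of it comes from using different people in the two medians. The last row shows that pairing does not protect against leaving that depends on follow-up itch.

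With complete data, the standard error of D is roughly 4% to 22% higher than that of P. The gap is widest when the SD of change is small.

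**5. Without any drop-out.** Month 2 scores 1, 2, 3, 4, 4, 6, 7, 8, 9 and Month 3 scores 2, 3, 4, 4, 4, 7, 8, 9, 10. Both medians are 4, so the group shift is 0. Yet 7 of 9 participants worsened by 1 point and the median own change is +1.

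**The case against.** Five objections deserve weight.

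- **Month 3 is an off-drug score.** A reader might infer that the measure says nothing about what happens once drug stops. The documents do not support that. Month 3 follows one month of wash-out, benefit remaining against baseline is a legitimate meaning of durability, and Section 7 reports Months 1, 2 and 3. The group-level shift from Month 2 to Month 3 follows by subtraction, provided the same people are used. What is absent is the within-participant contrast.
- **Durability has low standing.** A reader might infer that the abstract makes it a secondary aim. It does not. The abstract names the median change only, and durability appears as a clause in Section 10.C.
- **The drop-out case is constructed.** The excess of about 0.3 point needs the 4 highest-baseline participants to leave and the baseline median to keep them. The documents give no drop-out rate and do not say that different people will be used. This stands: the figure illustrates what the text permits and does not predict what will happen.
- **Pairing is no cure for informative loss.** This also stands. When leaving depends on follow-up itch, the paired median is inflated nearly as much.
- **The wording is loose.** It may have been meant as the median of participants' own changes. If so, one clarifying sentence settles that part, but the Month 2 to Month 3 change is still unspecified.

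**Conclusion.** The point holds as a minor one. Taken literally, the only analysis tied to durability is a shift between group medians against baseline. It discards the pairing, has no rule fixing who enters each median, and is not accompanied by a within-participant change from Month 2 to Month 3.

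Under the assumptions shown, the shift averages about 1.8 against a paired 1.5 if the 4 highest-baseline participants of 20 leave. It shows no upward bias under random loss, and its standard error is roughly 4% to 22% higher with complete data. For scale, Section 10.B treats 2 to 3 NRS points as the important difference, so 0.3 point is modest. These sizes depend on the assumed baseline distribution, SD of change and pattern of loss, none of which the documents give.

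It would go too far to conclude that the planned measure is invalid, or that drop-out must bias it. The primary responder endpoint is unaffected.

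**What to change.** In Sections 7 and 10.C:

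1. Replace the change in group median by the median of each participant's own change from baseline to Months 1, 2 and 3.
2. Add each participant's own change from Month 2 to Month 3 as the durability summary.
3. Report both by arm, with a confidence interval and the number of participants with both values.
4. Label the summary descriptive, and give the number missing by arm.

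The cost is one or two sentences in each section. No new data are needed if every participant receives a wash-out diary, as Section 9.D.v says. The Schedule of Events, as extracted, attaches to the Month 2 diary a footnote limiting it to those entering the open-label phase. That may be a table-reading artefact, but it should be checked against Section 9.D.v.

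The downside is that participants missing either value leave the summary, and it remains biased if leaving depends on follow-up itch. That is why the counts of missing scores belong beside it.
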